## 5.6 Randomization/Drug Assignment

All subjects will be assigned a unique identification number prior to dosing. This number will encode the subject's assignment according to the randomization schedule generated by the statistics department at AbbVie.

## 5.7 Protocol Deviations

The Investigator is responsible for complying with all protocol requirements, written instructions, and applicable laws regarding protocol deviations. Protocol deviations are prohibited except when necessary to eliminate an immediate hazard to study subjects. If a protocol deviation occurs (or is identified), the Investigator is responsible for notifying IEC/IRB, regulatory authorities (as applicable), and AbbVie.

# 6 SAFETY CONSIDERATIONS

## 6.1 Complaints and Adverse Events

### Complaints

A complaint is any written, electronic, or oral communication that alleges deficiencies related to the physical characteristics, identity, quality, purity, potency, durability, reliability, safety, effectiveness, or performance of a product/device. Complaints associated with any component of this investigational product must be reported to AbbVie.

### Medical Complaints/Adverse Events and Serious Adverse Events

An adverse event is defined as any untoward medical occurrence in a subject or clinical investigation subject administered a pharmaceutical product and which does not necessarily have a causal relationship with this treatment. An adverse event can therefore be any unfavorable and unintended sign (including an abnormal laboratory finding), symptom, or disease temporally associated with the use

of a medicinal (investigational) product, whether or not the event is considered causally related to the use of the product.

The investigators will monitor each subject for clinical and laboratory evidence of adverse events on a routine basis throughout the study. All adverse events will be followed to a satisfactory conclusion.

An elective surgery/procedure scheduled to occur during a study will not be considered an adverse event if the surgery/procedure is being performed for a pre-existing condition and the surgery/procedure has been pre planned prior to study entry. However, if the pre-existing condition deteriorates unexpectedly during the study (e.g., surgery performed earlier than planned), then the deterioration of the condition for which the elective surgery/procedure is being done will be considered an adverse event.

If an adverse event meets any of the following criteria, it is to be reported to MMV/PrimeVigilance as a serious adverse event within 24 hours of the site being made aware of the serious adverse event:

Death of Subject	An event that results in the death of a subject.
Life-Threatening	An event that, in the opinion of the investigator, would have resulted in immediate fatality if medical intervention had not been taken. This does not include an event that would have been fatal if it had occurred in a more severe form.
Hospitalization or Prolongation of Hospitalization	An event that results in an admission to the hospital for any length of time or prolongs the subject's hospital stay. This does not include an emergency room visit or admission to an outpatient facility.
Congenital Anomaly	An anomaly detected at or after birth, or any anomaly that results in fetal loss.
Persistent or Significant Disability/Incapacity	An event that results in a condition that substantially interferes with the activities of daily living of a study subject. Disability is not intended to include experiences of relatively minor medical significance such as headache, nausea, vomiting, diarrhea, influenza, and accidental trauma (e.g., sprained ankle).
Important Medical Event Requiring Medical or Surgical Intervention to Prevent Serious Outcome	An important medical event that may not be immediately life-threatening or result in death or hospitalization, but based on medical judgment may jeopardize the subject and may require medical or surgical intervention to prevent any of the outcomes listed above (i.e., death of subject, life threatening, hospitalization, prolongation of hospitalization, congenital anomaly, or persistent or significant disability/incapacity). Additionally, any elective or spontaneous abortion or stillbirth is considered an important medical event. Examples of such events include allergic bronchospasm requiring intensive treatment in an emergency room or at home, blood dyscrasias or convulsions that do not result in inpatient hospitalization, or the development of drug dependency or drug abuse.

All adverse events reported from the time of study drug administration until 30 days or 5 half-lives after discontinuation of study drug administration will be collected, whether solicited or spontaneously reported by the subject. In addition, serious adverse events and protocol-related non-serious adverse events will be collected from the time the subject signs the study-specific informed consent.

MMV/PrimeVigilance will be responsible for Suspected Unexpected Serious Adverse Reactions (SUSAR) reporting for the Investigational Medicinal Product (IMP) in accordance with global and local requirements.

### Adverse Events of Special Interest (AESI)

Adverse events will be monitored throughout the study to identify any of special interest that may indicate a trend or risk.

All the abnormalities listed below should be reported as an AESI:

- Related to hematotoxicity:
  - A fall in hemoglobin of  $> 20$  g/L or 25% from the baseline value,
  - A fall in absolute neutrophils count to  $< 1000/\text{mm}^3$ ,
  - A fall in platelet level to  $< 100,000/\text{mm}^3$ .
- Related to hepatotoxicity:
  - ALT or AST  $> 3 \times$  ULN with the appearance of worsening of fatigue, nausea, vomiting, fever, rash, or eosinophilia,
  - AST or ALT increase  $> 8 \times$  ULN,
  - ALT or AST rises rapidly to  $> 5 \times$  ULN in less than 4 weeks or persists for more than 2 weeks,
  - ALT or AST  $> 3 \times$  ULN and TBL  $> 2 \times$  ULN or INR  $> 1.5 \times$  ULN (Hy's Law if ALP  $< 2 \times$  ULN), to also be reported as an SAE in case of Hy's Law.
- Related to cardiotoxicity:
  - QTcF prolongation from baseline of  $> 60$  ms,
  - QTcF at any time  $> 450$  ms,
  - T wave liability, or T wave morphologic changes during therapy,
  - Bundle branch block, complete or partial,
  - Any arrhythmia.
- Related to dermatotoxicity, clinical signs of possible cutaneous adverse reactions such as:
  - Dermatitis,
  - Rash,
  - Erythematous rash,
  - Macular rash,

- Papular rash,
- Maculo-papular rash,
- Pruritic rash,
- Pustular rash,
- Vesicular rash.
- Related to pregnancy:
  - Pregnancy in subject or in partner of a male subject.

### Adverse Event Severity and Relationship to Study Drug

The investigator will rate the severity of each adverse event according to Common Terminology Criteria for Adverse Events (CTCAE, version 5.0).

The investigators will rate the severity of each adverse event as mild, moderate, or severe. The investigator will use the following definitions to assess the relationship of the adverse event to the use of study drug:

**Reasonable Possibility** – After consideration of factors including timing of the event, biologic plausibility, clinical judgment, and potential alternative causes, there is sufficient evidence (information) to suggest a causal relationship.

**No Reasonable Possibility** – After consideration of factors including timing of the event, biologic plausibility, clinical judgment, and potential alternative causes, there is insufficient evidence (information) to suggest a causal relationship.

### Pregnancy

While not an adverse event, pregnancy in a study subject must be reported to MMV/PrimeVigilance within 1 working day after the site becomes aware of the pregnancy. Subjects who become pregnant during the study must be discontinued from study procedures (Section 5.3). If a pregnancy occurs in a study subject or in the partner of a study subject, information regarding the pregnancy and the outcome will be collected.

In the event of pregnancy occurring in a subject's partner during the study, written informed consent from the partner must be obtained prior to collection of any such information. Pregnancy in a subject's partner will be collected from the date of the first dose through 120 days following the last dose of study drug.

The pregnancy outcome of an elective or spontaneous abortion, stillbirth or congenital anomaly is considered a serious adverse event (SAE) and must be reported to MMV/PrimeVigilance within 24 hours after the site becomes aware of the event.

## 6.2 Product Complaint

---

A product complaint is any complaint related to the biologic or drug component of the product or to the medical device component(s).

For a product this may include, but is not limited to, damaged/broken product or packaging, product appearance whose color/markings do not match the labeling, labeling discrepancies/inadequacies in the labeling/instructions (e.g., printing illegible), missing components/product, device not working properly, or packaging issues.

Product complaints concerning the investigational product and/or device must be reported to AbbVie within 1 business day of the study site's knowledge of the event. Product complaints occurring during the study will be followed up to a satisfactory conclusion.

## 7 STATISTICAL METHODS & DETERMINATION OF SAMPLE SIZE

### 7.1 Statistical and Analytical Plans

---

Completed and specific details of the statistical analysis will be described and fully documented in the Statistical Analysis Plan (SAP). The statistical analyses will be performed using SAS (SAS Institute Inc., Cary, NC, USA).

### 7.2 Statistical Analyses for Pharmacokinetics

---

#### Primary Analysis

For DSM265, an analysis of variance (ANOVA) will be performed for  $T_{max}$ ,  $\beta$ , the natural logarithms of  $C_{max}$ , AUC, and C168. Significant pharmacokinetic sample time deviations will be identified and listed.

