## 1 SYNOPSIS

Title: Relative Bioavailability and Effect of Food on DSM265-TPGS 34% SDD Powder in Healthy Adult Subjects	
Background and Rationale:	The current clinical formulation requires reconstitution/administration with a 240 mL sucralose-based vehicle (for a 400 mg adult dose). The new formulation was selected to dissolve in a smaller volume with water (approximately 60 mL for 400 mg adult dose).
Objectives and Endpoints:	The primary objective of this study is to compare the relative bioavailability of the oral DSM265-TPGS 34% SDD powder with the reference DSM265 25% SDD powder for suspension formulation. Another objective of the study is to evaluate the effect of food on the bioavailability of DSM265-TPGS 34% SDD powder.
Investigator(s):	[name]
Study Site(s):	AbbVie Clinical Pharmacology Research Unit (ACPRU)
Study Population and Number of Subjects to be Enrolled:	Approximately 42 healthy adult subjects
Investigational Plan:	This Phase 1, single-dose, open-label study will be conducted according to a randomized parallel group design in adult male and female subjects (3 groups of 14 subjects each). Subjects will be confined for 3 days with outpatient assessments through 21 days. Blood samples will be collected for 480 hours after dosing.
Key Eligibility Criteria:	Volunteers in general good health. Women must be of non-child bearing potential (WONCBP).
Study Drug and Duration of Treatment:	Single dose of 400 mg DSM265 25% SDD (Reference) Single dose of 400 mg DSM265 TPGS 34% SDD (Test)
Date of Protocol Synopsis:	13 August 2018

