#### Demographic

- ✓ 2. Male or female between 18 and 55 years of age inclusive at the time of screening.
- ✓ 3. Body Mass Index (BMI) is  $\geq 18.0$  to  $\leq 29.9$  kg/m^2 after rounding to the tenths decimal. BMI is calculated as weight in kg divided by the square of height measured in meters.

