## 8 ETHICS

### 8.1 Independent Ethics Committee/Institutional Review Board (IEC/IRB)

---

The protocol, informed consent form(s), recruitment materials, and all subject materials will be submitted to the IEC/IRB for review and approval. Approval of both the protocol and the informed

consent form(s) must be obtained before any subject is enrolled. Any amendment to the protocol will require review and approval by the IEC/IRB before the changes are implemented to the study. In addition, all changes to the consent form(s) will be IEC/IRB approved.

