## APPENDIX D. ACTIVITY SCHEDULE

The following table shows the required activities and time-points. The individual activities are described in detail in the Operations Manual ([Appendix E](#)).

Study Activities Table

Activity	Screening	Day -1 Initial Confinement	Day 1	Day 2	Day 4	Day 6	Day 8	Day 10	Day 14 +/- 1 day	Day 21 +/- 1 day or Premature Discontinuation
INTERVIEWS & QUESTIONNAIRES										
Informed consent	✓									
Eligibility criteria	✓	✓								
Medical/surgical history (update only upon initial confinement)	✓	✓								
Drug alcohol and nicotine use	✓									
Adverse event assessment	✓	✓	✓	✓	✓	✓	✓	✓	✓	✓
Prior/concomitant therapy	✓	✓			✓	✓	✓	✓	✓	✓
LOCAL LABS & EXAMS										
HAV-IgM, HBsAg, HCV Ab, HIV Ab	✓									
Height (Screening and Initial confinement only) and weight	✓	✓								✓
Physical examination	✓	✓		✓						✓
Drug, Alcohol and Cotinine Screen	✓	✓								
12-lead ECG single	✓	✓	✓	✓						✓
Vital signs	✓	✓	✓	✓	✓	✓	✓	✓	✓	✓
FSH test (postmenopausal women)	✓									
Pregnancy test (non-postmenopausal women) (u = urine; s = serum)	✓ (u)	✓ (s)								✓ (s)
Blood Chemistry Hematology (CBC), and Urinalysis	✓	✓		✓			✓			✓
Blood samples for DSM265 assay			✓	✓	✓	✓	✓	✓	✓	✓
Administration										
DSM265 Administration			✓							
Confinement		✓	✓	✓						

### Day 1

Day 1 Activity	Pre-Dose	0 Hour	0.5 Hour	1 Hour	2 Hour	4 Hour	6 Hour	8 Hour	12 Hour	24 Hour
Blood samples for DSM265 PK assay	✓		✓	✓	✓	✓	✓	✓	✓	✓
Study drug administration		✓								
12-lead ECG single						✓				
Vital signs	✓			✓		✓		✓	✓	✓

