## 3.7 Height and Weight

---

Height and weight will be measured in order to calculate body mass index (BMI). Body weight may be measured at additional timepoints throughout the study. The subject will wear lightweight clothing and no shoes during height measurement and weighing.

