## 6.4 Selection and Timing of Dose for Each Subject

---

The same dose will be administered to all subjects. Dosing will be accomplished in the morning of Study Day 1.

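### Does the primary ANOVA need body weight as a covariate, given a fixed dose and only 14 subjects per regimen?

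*Protocol*

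**What the plan says.** The Synopsis describes a "randomized parallel group design in adult male and female subjects (3 groups of 14 subjects each"), about 42 in all. Operations Manual Section 6.4 adds: "The same dose will be administered to all subjects". Operations Manual Section 6.3 has equal random allocation and mentions no stratification.

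Under Primary Analysis, Section 7.2 states that "an analysis of variance (ANOVA) will be performed for" Tmax, β and the log-transformed Cmax, AUC and C168. It lists no factors, covariates or contrasts. Section 7.1 says where these belong: "Completed and specific details of the statistical analysis will be described and fully documented in the Statistical Analysis Plan (SAP"). Sample size is left to the SAP as well.

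The Activity Schedule (Appendix D) has a row "Height (Screening and Initial confinement only) and weight", ticked at Screening, Day -1 and Day 21 or premature discontinuation. The Operations Manual gives the purpose: "Height and weight will be measured in order to calculate body mass index (BMI"). Section 5.1 admits men and women aged 18 to 55 with a BMI of 18.0 to 29.9 kg/m², where "BMI is calculated as weight in kg divided by the square of height measured in meters".

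**The concern.** Section 4.2 justifies parallel groups by the long half-life of DSM265, 85 to 112 hours. The price is that the formulation comparison (B against A) and the food comparison (C against B) are both made between subjects. A crossover would remove most of that variance. After a fixed dose, heavier subjects may well have lower exposure, and the BMI limits alone allow a 29.9/18.0 = 1.66-fold range of weight at a given height. Weight is known before dosing and costs nothing more to collect, yet the primary analysis does not mention it.

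If weight were strongly prognostic, leaving it out would make both intervals wider than necessary. Small groups could also differ in mean weight by chance and shift a ratio in a given trial. A covariate is credible only if it is fixed before concentrations are seen, so it is fair to ask the question at the planning stage.

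**Working it through.** **Design figure.** 3 × 14 = 42, which agrees with the stated total. The size cannot be derived further, because variability, error rates and any margin are left to the SAP.

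**Inputs from the protocol.** Three arms of 14, so 42 − 3 = 39 error degrees of freedom for a regimen-only model and 38 with one covariate.

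**Inputs that must be assumed, because the protocol gives none.** Between-subject CV 30, 40 or 50%. Standard deviation (SD) of log weight 0.12, 0.15 or 0.18; for comparison, a flat spread of log BMI between the limits gives ln(29.9/18.0)/√12 = 0.147. Exposure proportional to weight to the power −b, with b varied below.

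**Formulas.** With s = √ln(1 + CV²), the 90% half-width for a log ratio of two arms is

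- without covariate: t(0.95; 39) × s × √(2/14), with t = 1.6849;
- with covariate: t(0.95; 38) × s × √(1 − R²) × √(2/14) × √(1 + 1/37), with t = 1.6860.

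R² = (b × SD)² / ln(1 + CV²) is the share of log variance that weight explains. The factor √(1 + 1/37) is the average cost of chance imbalance in weight.

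**Cost if weight does not matter (R² = 0).** (1.6860/1.6849) × √(1 + 1/37) = 1.014, so the interval is about 1.4% wider.

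**Break-even.** 1 − 1/1.0141² = 0.028, a correlation of √0.0276 = 0.17 between log weight and log exposure. At an SD of 0.147 this needs b of at least 0.33, 0.44 or 0.53 for CV 30, 40 or 50%.

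**Middle case (CV 40%, b = 0.75, SD 0.15).** s = √ln(1.16) = 0.3853. The unadjusted half-width is 1.6849 × 0.3853 × √(2/14) = 0.2453, so an observed ratio of 1.00 has the interval exp(±0.2453) = 0.782 to 1.278. R² = 0.1125²/0.1484 = 0.085, and the multiplier is 1.014 × √0.915 = 0.970. The adjusted half-width is 0.2379, giving 0.788 to 1.269. In simulation (40,000 trials) the adjusted interval was the narrower one in 68% of trials for this case, and in 20% when weight had no effect.

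**Dependence on the assumed b.** The multiplier 1.0137 × √(1 − R²) was applied to every combination of the CVs and SDs above. (1.0137 is the exact mean cost; it also rounds to 1.014.)

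| Values of b allowed | Scenarios | Median change in half-width | Scenarios with a wider interval |
|---|---|---|---|
| 0.5, 0.75, 1 | 27 | 3.0% narrower | 3 |
| 0.25, 0.5, 0.75, 1 | 36 | 1.5% narrower | 12 |
| 0, 0.25, 0.5, 0.75, 1 | 45 | 0.5% narrower | 21 |

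In the first row the extremes are 0.6% wider and 20% narrower. Every scenario in that row assumes that weight matters, and the protocol favours none of the three rows over the others.

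**Validity.** Simulated coverage of the nominal 90% interval was 0.896 to 0.903 in all 27 scenarios of the first row, both with and without the covariate. Only precision differs.

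**The case for a change.** The strongest case for raising the point is that the trade looks asymmetric. The average cost is about 1.4% if weight is irrelevant, and the gain reaches about 20% if it is strongly prognostic. No new data are needed. Adjustment also removes chance imbalance: with a log-weight SD of 0.15, the difference in mean log weight between two arms has an SD of 0.15 × √(2/14) = 0.057. At b = 0.75, about one trial in ten would then have its ratio moved by at least exp(0.75 × 1.645 × 0.057) = 1.07, up or down. Finally, Section 7.2 does name ANOVA, so an SAP that adopted a weight-adjusted model should be reconciled with it.

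The arithmetic stands under its assumptions, and as advice to whoever writes the SAP it is reasonable. It does not show that the protocol is wrong. The 20% gain is one corner of an assumed grid, and the direction of the effect is unknown without a weight–exposure relation. The shift from chance imbalance is part of the between-subject variance that the unadjusted interval already allows for, which is why its coverage is correct. Nothing in the protocol singles out weight over sex or age, and both vary under the eligibility criteria.

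Changing Section 7.2 would not be free either: "Any amendment to the protocol will require review and approval by the IEC/IRB before the changes are implemented to the study". Putting a different primary model only in the SAP would invite the very discrepancy between the two documents that the argument wants to avoid.

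**Conclusion.** The concern does not hold. Section 7.2 names a valid type of analysis and lists no model terms. Section 7.1 assigns the details to the SAP, and covariate choice is an ordinary SAP detail. The SAP was not available here, so whether it includes weight is unknown, and silence in the protocol is not an omission.

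Only precision is affected. Depending on which weight effects one is willing to assume, the median gain is 0.5% to 3.0% of the 90% half-width, and the individual scenarios run from 1.4% wider (no weight effect) to 20% narrower. These figures rest wholly on assumed CVs, weight spreads and exponents. The protocol states no margin or decision rule, so no stated conclusion depends on the choice. Following the plan as written gives a sound analysis.

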#### Sample Size Estimation

Refer to the SAP for details on sample size determinations.

### 7.3 Statistical Analyses for Safety

---

Refer to the SAP for details on the safety analysis.

## 8 ETHICS

### 8.1 Independent Ethics Committee/Institutional Review Board (IEC/IRB)

---

The protocol, informed consent form(s), recruitment materials, and all subject materials will be submitted to the IEC/IRB for review and approval. Approval of both the protocol and the informed

consent form(s) must be obtained before any subject is enrolled. Any amendment to the protocol will require review and approval by the IEC/IRB before the changes are implemented to the study. In addition, all changes to the consent form(s) will be IEC/IRB approved.

## 8.2 Ethical Conduct of the Study

---

The study will be conducted in accordance with the protocol, Operations Manual, International Council for Harmonisation (ICH) guidelines, applicable regulations, and guidelines governing clinical study conduct and the ethical principles that have their origin in the Declaration of Helsinki. Responsibilities of the Investigator are specified in 0.

## 8.3 Subject Confidentiality

---

To protect subjects' confidentiality, all subjects and their associated samples will be assigned numerical study identifiers or "codes." No identifiable information will be provided to AbbVie.

# 9 SOURCE DOCUMENTS AND CASE REPORT FORM COMPLETION

The Investigator is responsible for ensuring the accuracy, completeness, legibility, and timeliness of the data reported. All source documents should be attributable, legible, contemporaneous, original, accurate, and complete to ensure accurate interpretation of data. Clinical site monitoring is conducted to ensure that the rights and well-being of human subjects are protected, that the reported trial data are accurate, complete, and verifiable, and that the conduct of the trial is in compliance with the currently approved protocol, ICH Good Clinical Practice (GCP), and applicable local regulatory requirement(s).

# 10 DATA QUALITY ASSURANCE

AbbVie will ensure that the clinical trial is conducted with a quality management system that will define quality tolerance limits in order to ensure human subject protection and reliability of study results. Data are generated, documented, and reported in compliance with the protocol, ICH GCP, and applicable regulatory requirements.

